2 INTRODUCTION

2.1 STUDY RATIONALE

Background: Hispanic women and children who become overweight or obese are at risk for developing prediabetes, type 2 diabetes, and cardiovascular disease later in life. Interdisciplinary interventions which target Hispanic women and their 3-5-year old children to improve nutrition and physical activity behaviors, manage adiposity and weight in mothers, and prevent excessive adiposity and weight gain trajectory in their children offer promise to break the intergenerational cycle.

Methods: Using a randomized two-group, repeated measures experimental design, the goal of the proposed study is to investigate the efficacy of a 12-week nutrition and physical activity program including education, coping skills training, and home-based intervention in Hispanic women and their 3-5-year old children. The program includes 6 months of continued monthly contact to help overweight and obese Hispanic mothers and their children improve adiposity, weight (trajectory for children), health behaviors (nutrition and physical activity), and self-efficacy. We will partner with two federally qualified health departments in Durham and Chatham counties, North Carolina to enroll participants. We will partner with community centers to deliver the intervention. A total of 294 Hispanic women with a $BMI > 25 \text{ kg/m}^2$ and 294 Hispanic 3-5-year old children with a $\geq 25^{\text{th}}$ BMI percentile will be enrolled over 4 years and randomized to the experimental or equal attention control group. Data will be collected at Time 1 (0 months [baseline]) to Time 2 (9 months [completion of the intervention]) and Time 1 to Time 3 (15 months [after 6 months with no contact from the study staff]). Data collected will include adiposity in mothers and children and weight (primary outcomes: BMI in mothers and BMI percentile in the children). Secondary outcomes will include health behaviors and self-efficacy in the mothers and in the children. We will also evaluate the cost of delivering the program for public health departments. We will use general linear mixed models to test the hypotheses.

Discussion: Decreasing overweight and obesity in Hispanic women and slowing adiposity and weight gain trajectory in young Hispanic children is urgently needed to decrease morbidity, mortality, and future health care costs.

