9.2 SAMPLE SIZE DETERMINATION

A total of 250 mother-child dyads, or 125 dyads in each randomized group, are expected to complete the study. However, we will enroll 294 mother-child dyads ($n = 588$ participants) or 147 dyads per group, to take into account a 15% attrition rate. Our previous studies with Hispanic mothers with limited English proficiency and their children have had attrition rates ranging from 9% to 15% [23, 33]. Power calculations were performed with POWERLIB20 SAS/IML modules, which incorporate methods described in Muller [39]. These methods calculate power for a general linear multivariate model that includes repeated measures data structures, of which a two-group longitudinal design is a special case. Power was calculated on the use of a separate multivariate model for each outcome addressed in the aims, incorporating measurements at all available time points. Effect size estimates were based on the pilot data [23], where estimated within-subject correlation and standardized mean difference were .25 and .53, respectively, for mothers' BMI and .30 and .59, respectively, for children's BMI percentiles. For each outcome, power was computed for a test of the time by treatment interaction at a two-sided significance level of .05. For an analyzable sample of 125 mother-child dyads per group (total of 250 mother-child dyads), calculated statistical power exceeds 95% for both the test of children's BMI percentiles in Aim 1 and the test of mothers' BMI in Aim 2; if the within subject correlations and standardized mean differences are lower than observed in the pilot at .20 and .45, respectively, statistical power will nonetheless exceed 80%. A formal power analysis was not conducted for Aim 3 because the focus is on estimation (rather than testing) of direct and indirect mediation effects. Nonetheless, based on Shrout and Bolger [40], a sample size of 80 to 85 should provide power in the 70% to 85% range to detect medium effects of the intervention on the mediator (e.g., maternal self-efficacy), and the mediator on the outcomes (e.g.,

mother's BMI) with a two sided .05 significance level. Our 250 dyads should provide an adequate sample to quantify mediation of the relevant variables.

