9.4 STATISTICAL ANALYSES

- 9.4.1 GENERAL APPROACH
- 9.4.2 ANALYSIS OF THE PRIMARY ENDPOINT(S)
- 9.4.3 ANALYSIS OF THE SECONDARY ENDPOINT(S)
- 9.4.4 SAFETY ANALYSES
- 9.4.5 BASELINE DESCRIPTIVE STATISTICS
- 9.4.6 PLANNED INTERIM ANALYSES
- 9.4.7 SUB-GROUP ANALYSES
- 9.4.8 TABULATION OF INDIVIDUAL PARTICIPANT DATA
- 9.4.9 EXPLORATORY ANALYSES 9.5
- 9.4.10 DATA ANALYSIS

Aim 1: To test the efficacy of the intervention in decreasing trajectory of adiposity and weight gain in 4-year-old children, separate mixed models will be used to test longitudinal differences between the intervention and control group means for each outcome across the study period. Mixed effects models, with a random intercept to account for between-mother or between-child differences, will be used for repeated measures analyses of each outcome (child BMI percentile, waist circumference, and triceps and subscapular skinfolds). The dependent variable will be the outcome at each of the three time points; the model will include time point (categorical), intervention group, and the interaction between the two. A test of this interaction will serve as the overall test of intervention effect, and step-down tests will be conducted to compare Time 2 and Time 3 to Time 1, and to estimate how or whether the intervention effect changed from Time 2 to Time 3, using a Hochberg correction to account for multiple comparisons [41, 42]. Results will be summarized through the least-squares means for each group at each time point and the mean difference and corresponding 95% confidence interval.

Aim 2: To test the efficacy of the intervention in decreasing adiposity and weight in mothers, we will fit mixed models analogous to those described for Aim 1 with each of the primary outcomes (mother's BMI and adiposity measures: waist circumference, and triceps and subscapular skinfolds) and secondary outcomes (child health behaviors: nutrition and physical activity, mother's health behaviors: nutrition and physical activity, and mother's self-efficacy: nutrition and physical activity).

Aim 3: To identify the mediators through which the intervention influences weight management in mother-child dyads, the approach of Shrout and Bolger [40] will be employed. This method, based on bootstrapping, builds on established mediation testing procedures, such as the Baron and Kenny approach [43] and the Sobel test [44]. Mediation analyses test pathways by which an explanatory variable (X) is theorized to influence the

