Exploratory Aim: Analyses will be performed on weight status, adiposity, health behavior, and self-efficacy to explore whether the intervention effects for mothers are similar for those who are overweight (BMI 25-29.9kg/m²) and those who are obese (BMI ≥ 30 kg/m²). The mixed models described for Aims 1 and 2 will be implemented for each of the weight status, adiposity, health behavior, and self-efficacy variables, with the addition of four explanatory variables to each model: an indicator for the obese group, the interaction between this indicator and the indicator variable for group membership, the interaction between this indicator and time, and the three-way interaction among the group indicator, obese indicator, and time. The hypothesis test for the three-way interaction as well as the obesity indicator by group indicator interaction jointly equal to zero will indicate whether the intervention effects are homogeneous across BMI ranges. For each outcome, differences will be calculated to test the effects of the intervention versus control group at each follow-up point separately for each BMI range. Similar analyses will be performed with groupings of children in the 25th-84.9th percentile (normal weight), 85th-94.9th percentile (overweight) and $\geq 95^{\text{th}}$ percentile (obese).

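### The exploratory comparison of child weight groups on BMI percentile mixes the intervention effect with the compression of the percentile scale; a supporting BMI z-score analysis would separate them cheaply.

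*Combined protocol and SAP*

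**What the plan says.** - Section 2.1 names the weight outcomes as "BMI in mothers and BMI percentile in the children". Sections 3 and 9.1 make child BMI percentile a primary outcome, together with waist circumference and skinfolds.
- Section 9.4.10, Aim 1, fits a random-intercept mixed model to each child outcome, listed as "child BMI percentile, waist circumference, and triceps and subscapular skinfolds". For the fixed effects, "the model will include time point (categorical), intervention group, and the interaction between the two".
- Section 9.4.10, Exploratory Aim, adds weight-group interactions for mothers, tests them jointly, and estimates effects separately in each BMI range. It then extends this to children: "Similar analyses will be performed with groupings of children in the" three percentile bands, 25th-84.9th, 85th-94.9th and 95th and above.
- Section 5.1 admits children from the 25th percentile upwards with no upper limit.
- The sensitivity analyses in section 9.4.10 cover site, cohort and imputation. No BMI z-score, transformation or other child BMI metric is planned anywhere.

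**The concern.** Percentile points are not equal units. Near the median, a given change in standardised BMI moves a child many points; above the 95th percentile it moves the child very few. The planned child comparison groups children by their position on this same scale and then compares effects measured in its points. An intervention that worked equally well in every child on the z scale would appear to work least in obese children. In a trial that aims to prevent excessive weight gain, that could be misread as lack of benefit in the heaviest children.

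**Working it through.** **1. The plan's own power figures.** Section 9.2 says "power was computed for a test of the time by treatment interaction at a two-sided significance level of .05", with 125 dyads per group. Assume three time points, equal correlations ρ, and a standardised difference d reached by Time 2 and held at Time 3 (the documents state no mean pattern). The noncentrality is then λ = (125/2) × (2/3) × d²/(1 − ρ) = 41.67 × d²/(1 − ρ), with 2 numerator degrees of freedom.

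| Case | d, ρ | λ | Power | Plan |
|---|---|---|---|---|
| Child BMI percentile | .59, .30 | 20.7 | 98.7% | above 95% |
| Mother BMI | .53, .25 | 15.6 | 95.0% | above 95% |
| Pessimistic | .45, .20 | 10.5 | 83.2% | above 80% |

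The figures reproduce under this pattern. The child effect was estimated in the pilot on BMI percentiles, so compression in a pilot-like sample is already inside the .59.

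**2. Compression at a point.** With percentile = 100Φ(z), a fall of δ from quantile q is 100 × [q − Φ(Φ⁻¹(q) − δ)] points. For δ = 0.2:
- From the 50th: 50 − 42.1 = 7.9 points.
- From the 85th: 5.2. From the 90th: 4.0.
- From the 95th: 95 − 92.6 = 2.4.
- From the 97th: 1.6. From the 99th: 0.7.

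**3. Compression by band.** Averaging that expression over each band, with percentiles spread evenly within it, gives:
- 25th-84.9th: 7.2 points.
- 85th-94.9th: 3.9 points (7.2/3.9 = 1.8 times smaller).
- 95th and above: 1.4 points (7.2/1.4 = about 5 times smaller).

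A simulation with normally distributed baseline z truncated at the 25th percentile, three case mixes and random change gave 6.2-6.8, 3.8-4.0 and 1.2-1.9 points. The ratios were 1.6-1.7 for overweight and 3.4-5.5 for obese children.

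With an assumed 60/20/20% split, the overall mean effect is 0.6 × 7.2 + 0.2 × 3.9 + 0.2 × 1.4 = 4.32 + 0.78 + 0.28 = 5.38 points. Normal-weight children supply 4.32/5.38 = 80% of it, and obese children 0.28/5.38 = 5%.

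**4. Homogeneity test.** Assumptions: 250 children, 60/20/20% split, SD of z change .5, the same z effect in every child. The test is a 2-df treatment by weight-group test on change at one follow-up, standing in for the planned joint test. Rejection rates at the 5% level:

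| z effect | Percentile, pooled variance | Percentile, separate band variances | z-score |
|---|---|---|---|
| None | about 1% | – | about 5-6% |
| 0.2 | about 7% | about 28% | about 5-6% |
| 0.3 | about 18% | about 50-55% | about 5-6% |

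The plan mentions no band-specific residual variance, so the pooled column is its ordinary reading. Its rate of about 1% with no effect is below nominal because percentile change varies far less in the heavier bands than the pooled variance implies.

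The rates depend heavily on the assumptions. With 20%, 33% or 43% of children at or above the 85th percentile and change SDs of 0.4 or 0.6, the pooled test on percentile rejected in 1-25% of runs at 0.2 z and 3-66% at 0.3 z. On z-score it stayed at 4-7%.

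**5. Overall Aim 1 test.** Simulated power, z-score against percentile, for a uniform z effect:
- 0.2 z, SD .6: 79% against 68-76%.
- 0.2 z, SD .5: 88% against 82%.
- 0.2 z, SD .4: about 99% against 96-98%.
- 0.1 z, SD .4: 52-53% against 43-46%.

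The loss is about 0 to 10 percentage points, because the SD of percentile change shrinks along with the effect.

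**The case against.** The strongest reply is that homogeneity always depends on the scale, and nothing in the documents makes an equal z effect the right definition of equal benefit. That stands: the point is conditional on this premise. The comparison is also exploratory, and the Exploratory Aim in sections 3 and 9.1 speaks only of mothers, so no efficacy claim rests on it. Waist circumference and skinfolds are primary child outcomes too and are not percentiles. Z-scores themselves compress at the extreme top.

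A reader might infer more than the documents support:
- **That Aim 1 is underpowered.** The pilot effect is on the percentile scale, the stated power reproduces, and the loss against a z-score model is modest. It could matter more if the trial enrols heavier children than the pilot did, but the pilot's weight distribution is not given.
- **That the planned test will find false heterogeneity.** With a pooled variance it rejects barely above nominal at 0.2 z and below nominal with no effect. The high rates need separate band variances, larger effects, or a heavier or less variable sample.
- **That the shrinkage is five-fold in all heavier children.** That fits the obese band only.
- **That it holds for the same change in weight.** The calculation fixes the z change. The documents give no growth-reference values with which to convert kilograms or BMI units.

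What survives does not depend on the test rejecting. The plan commits to band-specific estimates, and on percentile these will differ whenever the z effect is uniform and not zero.

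**Conclusion.** The exploratory child weight-group comparison on BMI percentile is confounded with the scale. Under a uniform z effect, the percentile effect looks about 1.6 to 1.8 times smaller in overweight children and roughly three to five times smaller in obese children. The homogeneity test on percentile is also poorly calibrated: too conservative with no effect, and above nominal by an amount that depends on effect size, case mix and variance handling when a uniform z effect exists. The band averages rest on the equal-z premise and the assumed spread within bands; the rejection rates also rest on the assumed case mix, change SD and effect sizes. This is a cheap improvement, not an error in the primary analysis or in the sample size.

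**What to change.** - Keep BMI percentile as the named child outcome and as the eligibility measure.
- Pre-specify the same mixed model on BMI z-score, from the same growth reference as the percentile, as a supporting Aim 1 analysis.
- Run the exploratory child weight-group comparison on z-score instead of percentile, leaving the bands as they are.

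Height and weight are already measured at all three times (sections 1.3 and 8.1), and the child's birthdate and gender are obtained at telephone screening (section 5.5), so no new data are needed. The cost is a second child weight result to report, with percentile remaining the named one. The report should add that z-scores also compress at the extreme top, so estimates in the heaviest children still need caution.

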6.3 MEASURES TO MINIMIZE BIAS: RANDOMIZATION AND BLINDING

After enrollment and baseline assessment, dyads will be randomized to either the intervention or control group using a computer-generated randomization table, stratifying by BMI group, overweight ($25 - 29.9 \text{ kg/m}^2$) and obese ($\geq 30 \text{ kg/m}^2$), and utilizing blocking to help ensure balance between the groups. Mothers will be informed of their group assignment by telephone. We have not included fathers, as in previous studies in this population, because the majority of fathers work 6 days a week and cannot attend class [7, 23]. Data collection research assistants will be blinded to group status.

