7.2 PARTICIPANT DISCONTINUATION/WITHDRAWAL FROM THE STUDY

Participants are free to withdraw from participation in the study at any time upon request.

An investigator may discontinue a participant from the study for lost-to-follow up and unable to contact subject.

The reason for participant discontinuation or withdrawal from the study will be recorded. Subjects who sign the informed consent form and are randomized but do not receive the study intervention may be replaced. Subjects who sign the informed consent form, and are randomized and receive the study intervention, and subsequently withdraw, or are discontinued from the study will not be replaced.

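### A free gain in precision, not an error: dyads are randomised after baseline, yet the Aim 1 and 2 models leave the Time 1 group difference free; a common Time 1 mean would cut the variance of the main contrasts by about 31% for child BMI percentile, and by less for mothers' BMI

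*Combined protocol and SAP*

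**What the plan says.** Section 9.4.10 specifies one mixed model per outcome. "The dependent variable will be the outcome at each of the three time points", and "the model will include time point (categorical), intervention group, and the interaction between the two". The models are fitted "with a random intercept to account for between-mother or between-child differences", which implies a single correlation across the three times. "A test of this interaction will serve as the overall test of intervention effect"; step-down tests compare Times 2 and 3 with Time 1, and the two follow-ups with each other, with a Hochberg correction. Aim 2 uses analogous models for mothers.

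Section 6.3 gives the order of events: "After enrollment and baseline assessment, dyads will be randomized to either the intervention or control group", stratified by the mother's BMI group.

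Section 9.2 supplies the planning values. "A total of 250 mother-child dyads, or 125 dyads in each randomized group, are expected to complete the study", out of 147 enrolled per arm. For the pilot, "estimated within-subject correlation and standardized mean difference were .25 and .53, respectively, for mothers' BMI"; the child BMI percentile values are .30 and .59, and the fallback values are .20 and .45.

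Section 9.3 includes all randomised subjects as randomised and considers only gender, age and income as covariates. The sensitivity paragraph of 9.4.10 adds site and says that all available data are used. Nothing adjusts for the baseline value of the outcome.

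**The concern.** Baseline precedes randomisation, so the true Time 1 means are equal across arms as long as every randomised dyad is analysed. The planned model nevertheless estimates a Time 1 group difference and, in effect, subtracts all of it from each follow-up difference. At the low correlations in 9.2, Time 1 says little about follow-up, so full subtraction adds more noise than it removes. A common Time 1 mean subtracts only the part that the correlation supports.

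At stake is the precision of the two main follow-up contrasts for outcomes already being measured. It matters most if the true effect is near the fallback size, or fades by Time 3, which follows six months without contact.

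**Working it through.** **Inputs.** From 9.2: 147 per arm at Time 1, 125 per arm at both follow-ups, and the correlations (rho) and standardised differences (d) above. From 9.4.10: compound symmetry and all available data. Variances are in units of 2/125, with outcome SD 1.

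**1. The plan's own power.** Take complete data on 125 per arm and a 2-df time x group test with F on 2 and 248 df. For a constant effect the noncentrality is 62.5 d² x 2 / [3(1 - rho)].
- Mothers' BMI: 62.5 x .2809 x 2 / 2.25 = 15.61, power .95.
- Child BMI percentile: 62.5 x .3481 x 2 / 2.10 = 20.72, power .987.
- Fallback: 62.5 x .2025 x 2 / 2.40 = 10.55, power .83.

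These agree with the plan's claims of above 95%, above 95% and above 80%, to rounding for mothers' BMI. An effect at only one follow-up gives the same figures.

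**2. Variance of Time 2 v Time 1, and of Time 3 v Time 1.**
- Planned: (1 - rho²) + (1 - rho)² x 125/147.
- Common Time 1 mean: 1 - rho².

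| rho | planned | constrained | cut |
|---|---|---|---|
| .20 (fallback) | .960 + .544 = 1.504 | .960 | 36% |
| .30 (child BMI percentile) | .910 + .417 = 1.327 | .910 | 31% |
| .50 (illustration) | .750 + .213 = .963 | .750 | 22% |
| .90 (illustration) | .190 + .0085 = .1985 | .190 | 4% |

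The Time 3 v Time 2 contrast gains nothing under compound symmetry.

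**3. Mothers' BMI.** Stratification already balances a share s of baseline variance, so the second planned term is multiplied by (1 - s). The documents give no s; assume .45 to .70.
- rho .25: s = .45 gives .263 / 1.201 = 22%; s = .70 gives .143 / 1.081 = 13%.
- rho .20: 24% and 15%.

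**4. Class clustering.** Classes hold 18-19 mothers, or about 125/8 = 15.6 completers. A class effect arises after Time 1, so it adds about 15.6 x ICC to both variances (class variance taken relative to, and added to, the individual variance). For child BMI percentile:
- assumed ICC .02: .417 / (1.327 + .312) = 25%;
- assumed ICC .10: .417 / (1.327 + 1.562) = 14%.

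**5. Smaller Time 1 SD.** Eligibility cuts off low BMI at Time 1. With Time 1 SD k times the follow-up SD, the second planned term is (k - rho)² x 125/147. At an assumed k = .8 and rho .30 it is .213, and the cut is .213 / 1.123 = 19%.

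**6. Power at 147/125, independent dyads.** Let a = (1 - rho)² x 125/147 for the planned model and 0 for the constrained one, A = 1 - rho² + a, B = rho - rho² + a, and let the effect be d at Time 2 and hd at Time 3. The noncentrality is 62.5 d² [(1 + h²)A - 2hB] / (A² - B²).

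| case | noncentrality, planned v constrained | power |
|---|---|---|
| fallback, constant (h = 1) | 11.46 v 22.60 | .86 v .99 |
| fallback, Time 2 only (h = 0) | 10.78 v 13.56 | .84 v .92 |
| fallback, halved at Time 3 (h = .5, assumed) | 8.42 v 14.69 | .74 v .94 |

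At the pilot values the planned model already has .96 (mothers, ignoring stratification) and .99 (children) with a constant effect, and .89 and .96 if the effect halves.

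**The case against.** The strongest reply is that this is a preference. The planned model is coherent, its overall test is the one that was powered, and that power reproduces. This stands. A reader might infer that the analysis is biased or underpowered, and the documents do not support that. Power below 80% appears only when the fallback values are joined to a halving by Time 3, a pattern that 9.2 does not state.

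A reader might also take 31-36% as the gain for every outcome. It is not. The only child correlation in 9.2 gives 31%; 36% belongs to the fallback; the .25 belongs to mothers' BMI, where stratification reduces the gain. Section 9.2 gives no correlation for waist, skinfolds or behaviours. Clustering and unequal variances shrink the gain further. These limits stand and are built into the conclusion.

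Finally, the constraint needs every randomised dyad in the analysis, while 7.2 says "Subjects who sign the informed consent form and are randomized but do not receive the study intervention may be replaced". One might infer that replaced dyads are dropped. Section 7.2 does not say so, and 9.3 includes all subjects as randomised. The point needs one clarifying sentence.

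**Conclusion.** The point holds as an optional improvement. Under compound symmetry, independent dyads and equal variances, a common Time 1 mean reduces the variance of the two baseline-referenced contrasts by about 31% for child BMI percentile, and by 36% at the fallback correlation. For mothers' BMI the reduction is roughly 13-24% if the strata carry 45-70% of baseline variance. For child BMI percentile it falls to about 25-14% at a class ICC of .02-.10, or to about 19% at a Time 1 SD ratio of .8; these three sets of inputs are assumptions. The gain also falls as the correlation rises.

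The practical benefit is protection in the fallback case. With a sustained effect at the pilot values there is little power left to gain. Class clustering affects both models and is not resolved by this change.

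**What to change.** In 9.4.10:
- Keep the categorical time terms, drop the group main effect, and keep group x Time 2 and group x Time 3.
- Define the overall test as the 2-df test that both group terms are zero. Step-down tests use the two terms and their difference, with Hochberg as planned.
- Preferably use an unstructured 3x3 covariance, since Time 1 variances may differ. It must replace the random intercept: the two together have 7 parameters, of which only 6 can be identified.
- State that all randomised dyads, including any replaced under 7.2, are analysed as randomised, as 9.3 already requires.

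In the Exploratory Aim, keep the obese indicator and obese x time, and add only obese x group at Time 2 and at Time 3, tested jointly on 2 df. The model then has 3 + 2 + 3 + 2 = 10 columns, all estimable, and Time 1 stays constrained. The child groupings follow the same pattern, with 4 df for three categories.

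The cost is wording and a few covariance parameters; no new data are needed. Model-based Time 1 means become identical across arms, so observed means must appear in the baseline table. The change should be made before any unblinded analysis. Site x time, stratum x time and the 9.3 covariate rule are separate, optional matters and not part of this change.

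### With the interaction test written as a binding gate, the Hochberg step over the three time contrasts is unnecessary; under a sustained effect it costs about 2 to 6 points of power per time point

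*Combined protocol and SAP*

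**What the plan says.** Section 9.4.10 (Aim 1) fits a separate mixed model to each child outcome, with time as a three-level factor, group, and their interaction. On testing it says: "A test of this interaction will serve as the overall test of intervention effect, and step-down tests will be conducted". The step-down tests set Time 2 and Time 3 against Time 1. The same sentence adds an estimate of how the effect changes from Time 2 to Time 3, and ends "using a Hochberg correction to account for multiple comparisons". Aim 2 uses analogous models for the mothers.

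Two things are not written. No clause makes the contrasts conditional on a significant interaction, and the members of the Hochberg family are not listed.

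Section 9.2 powers only the interaction: "power was computed for a test of the time by treatment interaction at a two-sided significance level of .05". It reports that "calculated statistical power exceeds 95% for both the test of children's BMI percentiles in Aim 1 and the test of mothers' BMI in Aim 2", and more than 80% in a fallback with correlation .20 and standardized difference .45. It gives no power for the Time 2 or Time 3 contrasts, although Aims 1 and 2 (Sections 3 and 9.1) are worded as exactly those two comparisons.

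**The concern.** With three time points the interaction has 2 degrees of freedom, and the three contrasts are the pairwise differences among three time-specific group differences. They span two dimensions, not three. A 2-df test at .05 followed by a three-way Hochberg correction therefore guards twice against the same event. The cost falls on the comparisons that the aims name, and it cannot be seen in Section 9.2, which reports power for the overall test only.

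**Working it through.** **Inputs (Section 9.2).** Two-sided alpha .05; n = 125 per group analyzable; standardized difference d and within-subject correlation ρ: mothers' BMI .53 and .25, child BMI percentile .59 and .30, fallback .45 and .20. **Assumed, not in the plan:** group difference 0 at Time 1, d at Time 2 and d at Time 3 (a sustained effect), d in outcome-SD units, compound symmetry.

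**1. The plan's own figure.** The interaction noncentrality is λ = Σ(d_t − mean d)² / [(2/n)(1 − ρ)]. For (0, d, d) the sum is 2d²/3, so λ = n d² / [3(1 − ρ)].

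- Mothers: 125 × .2809 / 2.25 = 15.6; power 95.0–95.2%.
- Children: 125 × .3481 / 2.10 = 20.7; power 98.7–98.8%.
- Fallback: 125 × .2025 / 2.40 = 10.5; power 83.2–83.7%.

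The ranges cover the chi-square, univariate F (2, 496 df) and multivariate F (2, 247 df) versions. The stated >95% and >80% reproduce.

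**2. Why the gate is enough within an outcome.** Let δ1, δ2, δ3 be the group differences at the three times. The hypotheses are δ2 = δ1, δ3 = δ1 and δ3 = δ2. Any two together give δ1 = δ2 = δ3, which is the interaction null. Every intersection is therefore tested by the 2-df test at .05. By the closed testing principle, each contrast can then be tested at .05 once that test is significant. This procedure also rejects everything that gated Hochberg rejects, because Hochberg never rejects a contrast whose raw p-value exceeds .05.

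**3. Family-wise error within one outcome (simulated).**

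| Procedure | Global null |
|---|---|
| Gate, contrasts at .05 | 5.0% |
| Gate, Hochberg over three | 4.3% |
| No gate, Hochberg over three | 4.4–4.5% |
| No gate, contrasts at .05 | 12.2% |

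With one contrast null and the other two not, gate plus unadjusted contrasts also gives 5.0%.

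**4. Power at each of Time 2 and Time 3, sustained effect (400,000 simulated trials per scenario).**

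| Scenario | Gate, .05 | Gate, Hochberg over three | Loss (points) |
|---|---|---|---|
| Mothers' BMI | 91.2% | 87.4% | 3.8 |
| Fallback | 75.8% | 69.5% | 6.3 |
| Child BMI percentile | 97.1% | 95.4% | 1.7 |

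Power to show an effect at both times falls from 87.3% to 80.8% (mothers) and from 68.3% to 57.9% (fallback).

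**5. Sensitivity of the loss.**

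- Half the effect gone by Time 3: at Time 3, 27.5% v 20.8% (fallback) and about 39.5% v 32.6% (mothers); at Time 2 the loss is 3.2 and 1.9 points.
- A quarter gone by Time 3: the fallback loses 8.6 points at Time 3, the largest loss found.
- d in change-score SD units, sustained effect: the loss is 1.1 (mothers), 3.2 (fallback) and about 0.3 (children).
- Gate, with Hochberg over the two baseline comparisons only: the loss is 0.02 points or less under the sustained effect and at most about 1 point under the waning or growing patterns.

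**The case against.** The strongest case against is that the plan states neither condition on which the argument rests.

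**The gate.** The words suggest an overall test followed by conditional tests, but no clause says so. If the contrasts run whatever the interaction shows, Hochberg is the only protection within an outcome and is not redundant: without it the error is 12.2%. This stands, and it is why the gate must be written. It does not remove the gain. Ungated Hochberg over three contrasts has per-time-point power of about 87.4% (mothers) and 69.6% (fallback), still below the gated .05 test.

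**The family.** The Time 3 v Time 2 contrast is framed partly as estimation, so the family may hold two contrasts. With the gate, the loss then all but vanishes. Without the gate, two-contrast Hochberg has slightly more power than the proposed rule under a sustained effect: 77.6% v 75.8% (fallback) and 91.9% v 91.2% (mothers). On that reading the change would cost about 1 to 2 points. This also stands. The sentence as printed attaches the correction to all three contrasts, which is why that reading is preferred here.

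**Preference.** A prespecified conservative correction is a legitimate choice. Agreed: nothing in the plan is invalid on this point.

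**Across outcomes.** Hochberg is the only multiplicity adjustment the plan names, and several primary measures are tested in children and mothers. As written, though, it follows the contrasts within each outcome's model, and nothing in the text extends it across outcomes.

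**Conclusion.** The point holds as a free improvement in efficiency. On the natural reading of Section 9.4.10, Hochberg over three contrasts is unnecessary once the interaction test is a binding gate. It costs about 4 points of power per time point for mothers' BMI, 6 in the fallback and 2 for child BMI percentile. These sizes rest on a sustained effect in outcome-SD units with compound symmetry. Under other patterns and scales the loss is roughly 1 to 9 points for mothers' BMI and the fallback, with smaller values possible for children.

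Three stronger conclusions might be inferred, and the documents support none of them.

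- That the planned analysis is flawed in error control: it is conservative, at about 4.3–4.5%.
- That the power claims in Section 9.2 are overstated: they concern the interaction test only, reproduce under the sustained pattern, and are untouched by Hochberg.
- That Hochberg can simply be deleted: that is safe only with a gate, which the plan does not state.

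**What to change.** In Section 9.4.10, replace the Hochberg clause with a rule to this effect: within each outcome, the contrasts Time 2 v Time 1, Time 3 v Time 1 and Time 3 v Time 2 are tested at two-sided .05 only if the 2-df time-by-group interaction is significant at .05; otherwise they are reported as estimates with confidence intervals and no claim of significance. Describe this as a closed test, and state that Aim 2 follows the same rule.

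If the sponsor prefers to keep Hochberg, the section should at least say whether the contrasts are gated and which of them form the family.

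The change needs no participants or data, only wording settled before unblinded analysis. It does add a rule: a contrast with p below .05 no longer counts when the interaction is not significant. If an ungated two-contrast Hochberg was intended, the change costs about 1 to 2 points of power under a sustained effect. Multiplicity across the several primary outcomes is a separate matter that this change does not address.
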